## **2. LIST OF ABBREVIATIONS**

See Medicine Glossary:

<http://glossary>

Term	Definition / description
ALT	Alanine Aminotransferase
AST	Aspartate Aminotransferase
AUC 0-tz	Area under the concentration-time curve of BI 754132 in serum over the time interval from 0 to the last quantifiable drug concentration
AUC 0-∞	Area under the concentration-time curve of BI 754132 in serum over the time interval from 0 extrapolated to infinity
BCVA	Best Corrected Visual Acuity
BLRM	Bayesian Logistic Regression Model
BMI	Body mass index
CI	Confidence Interval
C max	Maximum serum concentration of BI 754132 after a single intravitreal dose
CV	Arithmetic Coefficient of Variation
DBLM	Database Lock Meeting
DILI	Drug induced liver injury
DLE	Dose Limiting Event
ENR	Enrolled set
ERG	Electroretinography
ES	Entered set
FAF	Fundus autofluorescence
gCV	Geometric Coefficient of Variation
gMean	Geometric Mean
IVT	intravitreal
IQRMP	Integrated Quality and Risk Management Plan
Max	Maximum
Min	Minimum
N	Number non-missing observations
NAION	Nonarteritic anterior optic ischaemic neuropathy
OCT	Optical Coherence Tomography
P10	10 th percentile

Term	Definition / description
P90	90 th percentile
PKS	PK parameter analysis set
Q1	1 st quartile
Q3	3 rd quartile
q4w	4-weekly interval
RAGe	Report Appendix Generator system
REP	Residual Effect Period
SD	Standard Deviation
SMC	Safety Monitoring Committee
t max	Time from dosing to maximum serum concentration of BI 754132
TS	Treated Set
TSAP	Trial Statistical Analysis Plan
ULN	Upper Limit of Normal

### **3. INTRODUCTION**

As per ICH E9 ([1](#)), the purpose of this document is to provide a more technical and detailed elaboration of the principal features of the analysis described in the protocol, and to include detailed procedures for executing the statistical analysis of the primary and secondary variables and other data.

This trial statistical analysis plan (TSAP) assumes familiarity with the Clinical Trial Protocol (CTP), including Protocol Amendments. In particular, the TSAP is based on the planned analysis specification as written in CTP Section 7 “Statistical Methods and Determination of Sample Size”. Therefore, TSAP readers may consult the CTP for more background information on the study, e.g., on study objectives, study design and population, treatments, definition of measurements and variables, planning of sample size, randomisation.

Study data (including data entered in the RAVE EDC system and external data provided by suppliers) will be stored in a Clinical Data Repository (CDR).

Pharmacokinetic (PK) parameters will be calculated using Phoenix WinNonlinTM software (version 6.3 or higher, [REDACTED]).

The statistical analyses will be performed within the validated working environment CARE, including SAS® (current Version 9.4, by [REDACTED]), and a number of SAS®-based tools (e.g., macros for the analyses of AE data or laboratory data; Report Appendix Generator system (RAGe) for compilation/formatting of the CTR appendices).

#### **4. CHANGES IN THE PLANNED ANALYSIS OF THE STUDY**

All analyses as planned in the CTP will be performed and are described in more detail in this TSAP. The following changes compared to the protocol will be made:

- The additional analysis set 'Enrolled set' was defined, which is used for disposition tables and listings, see [Section 6.3](#).
- The additional analysis set 'Entered set' was defined, which is used in disposition tables and listings, see Section 6.3.
- The additional analysis set 'DLE evaluable set' was defined for the SRD part, which is used for SMC outputs related to the BLRM, see Section 6.3.

## 5. ENDPOINTS

### 5.1 PRIMARY ENDPOINTS

#### Section 2.1.2 of the CTP:

SRD part:

- *Number of patients with ocular (in the study eye) and systemic dose limiting events (DLEs) from drug administration until end of trial (EOT).*

For definition of a DLE, refer to [Section 7.4](#).

MD part:

*Number of patients with drug-related AEs from drug administration until EOT.*

### 5.2 SECONDARY ENDPOINTS

#### 5.2.1 Key secondary endpoints

This section is not applicable as no key secondary endpoints have been defined in the CTP.

#### 5.2.2 Secondary endpoints

#### Section 2.1.3 of the CTP:

[figure not shown]
SRD part:

- *Number of patients with drug-related AEs from drug administration until EOT*
- *Number of patients with any ocular AEs in the study eye from drug administration until EOT*
- *Cmax (maximum serum concentration of BI 754132 after a single intravitreal dose)*
- *AUC0-∞ (area under the concentration-time curve of BI 754132 in serum over the time interval from 0 extrapolated to infinity)*
- *tmax (time from dosing to maximum serum concentration of BI 754132)*

MD part:

- *Systemic exposure of BI 754132 after multiple IVT doses by determination of Cmin,1 and Cmin,2 (trough levels before second and third administrations) and serum concentrations 4, 8 and 14 weeks after the third administration*

The pharmacokinetic parameters listed in Section 2.1 of the CTP for drug BI 754132 will be calculated according to the BI Standard Operating Procedure (SOP) 'Standards and processes for analyses performed within Clinical Pharmacokinetics/Pharmacodynamics' [BI-KMED-TMCP-HTG-0025] ([7](#)). General note: PK parameters (planned as secondary or further endpoints) are determined only if sufficient data is available.

## **6. GENERAL ANALYSIS DEFINITIONS**

### **6.1 TREATMENTS**

For basic study information on investigational products, assignment of treatment and selection of doses, please see CTP, Section 4.

The study will be performed as a non-randomized, open-label trial in an uncontrolled manner.

It is planned that up to 24 patients (in SRD part it is expected to enrol up to 18 patients (planned 15 plus 3 additional if DLEs occur), in MD part it is expected to enroll 6 patients) with geographic atrophy secondary to age-related macular degeneration participate in this study, according to 4 sequential groups comprising 3 patients per group and 6 at final treatment group (SRD part) and 6 in MD treatment group.

For details of dosage and formulation see Table 6.1:1 below.

Table 6.1: 1 Labels for treatments for use in the CTR

Part	Treatment group	Treatment		Short label
SRD	1	A	BI 754132, injection, 0.3 mg	BI 0.3mg
SRD	2	B	BI 754132, injection, 1 mg	BI 1mg
SRD	3	C	BI 754132, injection, 3 mg	BI 3mg
SRD	4	D	BI 754132, injection, 6 mg	BI 6mg
MD	5	E	BI 754132, injection, 6 mg, q4wk	BI 6mg q4wk

#### **CTP Section 7.2.5:**

*For BI 754132, the residual effect period (REP) after IVT administration is not known. Therefore, all AEs with an onset between start of treatment and the respective EOT visit will be assigned to the on treatment period for evaluation.*

The following separate study phases will be defined for the analyses of AEs:

- **Screening** (ranging from 0:00h (midnight) on day of informed consent until first administration time of BI 754132)
- **On treatment**
  - **BI treatment** (separately for each treatment, ranging from the time of first administration of BI 754132 until 0:00h (midnight) on the day after trial completion date)

Please note that all AEs reported between start of trial drug administration and the last per-protocol contact will be considered on treatment (i.e. no follow-up period is considered in this trial).

The following AE displays will be provided in the report:

Section 15.3 and Appendix 16.1.13.1.8 (for ClinicalTrials.gov and EudraCT) of the CTR displays:

In these displays, the on treatment phase will be analysed (labelled with the short label of the study treatment). Screening will not be included in this analysis.

The following totals will be provided in addition in Section 15.3:

- a total over all on treatment phases included in this analysis ("Total") (SRD part only)

In Section 15.4 and Appendix 16.2 (Listings) of the CTR displays, the screening period will be included and no totals will be provided.

For detailed information on the handling of the treatments refer to Technical TSAP ADS (analysis data set) plan and Analysis Data Reviewers guide.

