### 7.2.5 Safety analyses

Adverse events will be coded using the Medical Dictionary for Drug Regulatory Activities (MedDRA). Standard BI summary tables and listings will be produced. For BI 754132, the residual effect period (REP) after IVT administration is not known. Therefore, all AEs with

an onset between start of treatment and the respective EOT visit will be assigned to the on-treatment period for evaluation. The safety analysis will be performed by planned dose group.

All treated patients will be included in the safety analysis. In general, safety analyses will be descriptive in nature and will be based on BI standards. No hypothesis testing is planned.

Statistical analysis and reporting of adverse events will concentrate on treatment-emergent adverse events, i.e. all adverse events occurring between start of treatment and the EOT visit. Adverse events that start before first drug intake and deteriorate under treatment will also be considered as ‘treatment-emergent’.

Frequency, severity, and causal relationship of adverse events will be tabulated by system organ class and preferred term after coding according to the current version of the Medical Dictionary for Drug Regulatory Activities (MedDRA) at database lock.

Laboratory data will be analysed both quantitatively as well as qualitatively. The latter will be done via comparison of laboratory data to their reference ranges. Values outside the reference range as well as values defined as clinically relevant will be summarised. Treatment groups will be compared descriptively with regard to distribution parameters as well as with regard to frequency and percentage of patients with abnormal values or clinically relevant abnormal values.

Vital signs, physical examinations, or other safety-relevant data observed at screening, baseline, during the course of the trial and at the end-of-trial evaluation will be assessed with regard to possible changes compared to findings before start of treatment.

A centralised evaluation of all 12-lead ECGs recordings (see [Section 5.2.6](#)) will be the basis for the ECG variables QT, HR, QTcF, PR, QRS, RR, and further derived ECG endpoints. The baseline value of an ECG variable is defined as the mean of the ECG measurements prior to drug administration. The derivation of the quantitative and qualitative ECG endpoints and their analyses will be described in the TSAP.

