### **7.8.1 Adverse Events**

AEs will be coded with the most recent version of MedDRA. The version to be used will be specified in RPM and will be displayed as a footnote in the respective output.

The analyses of AEs will be descriptive in nature and will be based on BI standards as presented in “Analysis and Presentation of Adverse Event Data from Clinical Trials – Display Template” [BI-KMED-BDS-HTG-0041] ([8](#)).

The standard AE analyses will be based on the number of patients with AEs (and not on the number of AEs).

The analysis of AEs will be based on the concept of treatment emergent AEs. That means that all AEs will be assigned to ‘screening’ or ‘on treatment’ phases as defined in [Section 6.1](#).

According to ICH E3 ([9](#)), in addition to Deaths and serious adverse events, ‘other significant’ AEs need to be listed in the clinical trial report. These will be any non-serious adverse event

that led to an action taken with study drug (e.g. discontinuation or dose reduced or interrupted).

An overall summary of adverse events (including number of patients with any AE, DLEs, drug related AEs, ocular AEs, AESIs, serious AEs, other significant AEs and drug related serious AEs) will be presented.

The frequency of patients with AEs will be summarised by treatment, primary system organ class (SOC) and preferred term (PT). Separate tables will be provided for patients with serious AEs, for patients with drug-related AEs, for patients with drug-related serious adverse events, for patients with ocular AEs, for patients with DLEs and for patients with AESIs. In addition, the frequency of patients with AEs will be summarised by treatment, worst intensity, primary system organ class (SOC) and preferred term (PT).

The SOCs will be sorted by default alphabetically, PTs will be sorted by frequency (within SOC).

According to the clinical study protocol, adverse events of special interest (AESI) will be analysed:

**Section 5.2.8.1.4 of the CTP:** *The following are considered as AESIs:*

- Hepatic injury  
*A hepatic injury is defined by the following alterations of hepatic laboratory parameters:*
  - *an elevation of AST (Aspartate Aminotransferase) and/or ALT (Alanine Aminotransferase)  $\geq 3$ -fold ULN combined with an elevation of total bilirubin  $\geq 2$ -fold ULN measured in the same blood sample, or*
  - *aminotransferase (ALT, and/or AST) elevations  $\geq 10$  fold ULN*

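### SAP 6.1 and 7.8.1 define treatment-emergent AEs by time window alone and leave out the protocol's rule for AEs that start before dosing and worsen afterwards; SAP 4 does not declare the difference

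*SAP*

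**What the plan says.** Protocol 7.2.5 builds the treatment-emergent definition in two parts. The first covers "all adverse events occurring between start of treatment and the EOT visit". The second extends it: "Adverse events that start before first drug intake and deteriorate under treatment will also be considered as" treatment-emergent.

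SAP 7.8.1 keeps the term: "The analysis of AEs will be based on the concept of treatment emergent AEs". It then explains the term by phase assignment: "That means that all AEs will be assigned to" either the screening or the on-treatment phase as defined in SAP 6.1.

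SAP 6.1 defines both phases by clock time. Screening runs from the day of consent to first administration, and on treatment runs from first administration to the end of the day of trial completion. The section reproduces the onset-based sentence of Protocol 7.2.5 but not the sentence on deterioration. It adds that "all AEs reported between start of trial drug administration and the last per-protocol contact will be considered on treatment". For the CTR Section 15.3 tables and the ClinicalTrials.gov and EudraCT displays it states: "Screening will not be included in this analysis". For Section 15.4 and Appendix 16.2, "the screening period will be included and no totals will be provided".

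SAP 4 says "All analyses as planned in the CTP will be performed and are described in more detail in this TSAP" and lists three changes. All three are added analysis sets, and none concerns AEs.

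**The concern.** The protocol and the SAP give different answers for one kind of event: an AE with onset after consent and before first dose that gets worse after the injection. Under the protocol it is treatment-emergent. Under the SAP's explicit assignment rule it sits in the screening window and drops out of the summary tables.

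Such events can exist because AEs are collected from consent (Protocol 5.2.8.2.1) and the screening visit may precede dosing by up to 28 days (Flow Charts I and II). The definition matters because it feeds the MD primary endpoint and both SRD secondary safety endpoints, which are patient counts in very small groups without a control arm.

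**Working it through.** There is no planned figure to reproduce. Both trial parts are analysed descriptively (Protocol 7.1, 7.2.2), and the MD sample of 6 does not come from a power calculation (Protocol 7.5). The check is a comparison of texts, followed by the size of one reclassified patient.

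**1. The two rules applied to the same event** (onset between consent and first dose, worsening after first dose, kept as one record)

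| Step | Protocol 7.2.5 | SAP 6.1 and 7.8.1, read literally |
|---|---|---|
| Is it treatment-emergent? | Yes, by the deterioration clause | No, onset falls in the screening window |
| CTR Section 15.3 summaries and registry displays | Counted | Not counted |
| CTR Section 15.4 and Appendix 16.2 | Not addressed | Shown, since screening is included there |

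**2. Which records are exposed**

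- Clinically significant ophthalmological findings at Visit 1 are baseline conditions (Protocol 6.2.1.1, 6.2.2.1).
- Worsening of the underlying disease or of another pre-existing condition is recorded as an AE (Protocol 5.2.8.1.1), as is clinically significant worsening in the ophthalmological safety assessments (Protocol 5.2.4). After dosing, such an AE would naturally carry a post-dose onset and is safe under either rule.
- What remains is an AE that arose between consent and first dose and stays a single record after it worsens. The documents do not say whether worsening of such an AE is entered as a new record.

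**3. When an endpoint changes**

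- MD primary endpoint and SRD drug-related AE endpoint: only if the event is judged drug-related and the patient has no other drug-related AE on treatment.
- SRD study-eye ocular AE endpoint: only if the event is ocular, in the study eye, and the patient has no other study-eye ocular AE on treatment. Relatedness is not needed.

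**4. Size of one patient** (100/n percentage points)

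- MD part, n = 6: 100/6 = 16.7
- SRD cohort of 3: 100/3 = 33.3
- SRD total, n = 3 + 3 + 3 + 6 = 15: 100/15 = 6.7

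**5. Chance of at least one affected MD patient.** The documents give no rate, so p, the per-patient probability of an event that changes the MD primary count, is an assumption. With 1 − (1 − p)^6:

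| Assumed p | At least one of 6 |
|---|---|
| 1% | 5.9% |
| 2% | 11.4% |
| 5% | 26.5% |
| 10% | 46.9% |

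These figures illustrate scale. They are not an estimate for this trial.

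**The case against.** The strongest reply is that nothing has been removed. SAP 3 presents the SAP as an elaboration of Protocol Section 7 and assumes the reader knows it. SAP 4 promises every protocol analysis, and SAP 7.8.1 invokes a concept that Protocol 7.2.5 already defines. On that view the deterioration clause applies and was simply not repeated. This stands in part: the documents do not show a decision to drop the rule. But SAP 7.8.1 says what the concept means for assignment, and a general promise does not tell a programmer to override that. Whether the rule was dropped or kept but not implemented, the text needs correcting.

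Three further points stand and narrow the matter. The recording rules for baseline conditions and ophthalmological worsening cover much of what might be feared. Protocol 5.2.8.1.6 lists pre-treatment cases among the arguments against causality, so a single record with a pre-dose onset is less likely to be judged drug-related. The Technical TSAP and the sponsor's AE display standard, which are not available here, may contain the derivation.

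A reader might infer three stronger things that the documents do not support:

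- That these events disappear from all AE output. They do not, because Section 15.4 and Appendix 16.2 include the screening phase.
- That any error can only lower the counts. The time windows do push that way, but SAP 6.1 says *reported* where the protocol sentence it reproduces uses onset. Taken literally, *reported* could pull in a pre-dose event first reported after dosing, so misassignment could go in either direction.
- That the SRD AE rate predicts the number of affected events. It could only suggest how many AEs begin in screening, not how many worsen, are judged related and are the patient's only such event.

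**Conclusion.** The point holds in a narrow form. The SAP's operative definition conflicts with Protocol 7.2.5 for AEs that start before first dosing and deteriorate afterwards, and SAP 4 does not declare it. The consequence is confined to the Section 15.3 and registry displays and to the endpoints built on the same assignment. It arises only for AEs with onset between consent and first dose that remain one record.

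One affected patient moves the MD primary endpoint by 16.7 points, for example from 0/6 to 1/6. How often this would happen cannot be derived from the documents. The conclusion rests on two assumptions: that the programming follows SAP 6.1 and 7.8.1 as written, and that worsening of such an AE is not entered as a separate record. The endpoint wording, which runs from drug administration to EOT, does not itself say whether onset or worsening is what counts, so the treatment-emergent definition decides it.

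**What to change.** In SAP 6.1 and 7.8.1, state that an AE with onset before first administration that deteriorates afterwards is assigned to on treatment, as in Protocol 7.2.5, with the date of worsening as the assignment date. Say how that date is obtained from the recorded data. In SAP 6.1, replace *reported* with *with onset*, so that the SAP sentence agrees with the protocol sentence above it. If the sponsor prefers assignment by time window alone, list that in SAP 4 as a departure from Protocol 7.2.5, with a reason.

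The cost is a sentence or two in the SAP and one derivation rule in the analysis data set. No sample size, visit or assessment changes. No change to data entry is proposed for the SRD part: Protocol 1.2 reports its 15 patients as having completed, so the rule would be applied there to the data as recorded.

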## **6.2           IMPORTANT PROTOCOL DEVIATIONS**

Data discrepancies and deviations from the CTP will be identified for all treated patients.

**Section 7.2.1.2 of the CTP:** *Important protocol deviations (iPDs) will be defined in the Integrated Quality and Risk Management (IQRM) plan. iPDs will be identified no later than in the Report Planning Meeting, and the iPD categories will be updated as needed.*

Consistency check listings (for identification of deviations of time windows) and a list of protocol deviations (e.g. deviations in drug administration, in blood sampling times, etc.) will be provided to be discussed at the Report Planning Meeting and database lock meeting (RPM/DBLM). At this meeting, all manual deviations identified at the sites by the CRAs and deviations too complex to program will be reviewed by the trial team to decide which are considered important. For definition of important protocol deviations (iPD), and for the process of identification of these, refer to the Boehringer Ingelheim (BI) SOP "Identify and Manage Important Protocol Deviations (iPD)" (2).

iPDs will be identified no later than in the Report Planning Meeting. If any iPDs are identified, they are to be summarised into categories and will be captured in the RPM/DBLM minutes (decision log) and in the iPD specification file (3). The iPD categories in the iPD specification file will be updated as needed. The decision on exclusion of subjects from analysis sets will be made after discussion of exceptional cases and implications for analyses. The iPD specification file (e.g. the DV domain specifications) will be stored within the TMF in EDMS.

The iPDs will be summarised and listed.

### **6.3 SUBJECT SETS ANALYSED**

- **Enrolled set (ENR):**  
This subject set includes all patients who were enrolled in the study (i.e. signed informed consent) regardless of whether they were treated or not. The ES is used for the disposition table / listing.
- **Entered set (ES):**  
This subject set includes all patients who signed informed consent and were entered in the study regardless of whether they were treated or not. The ES is used in the disposition table / listing.
- **Treated set (TS):**  
The TS will consist of all patients who were treated with at least one dose of BI 754132. This is the full analysis set population in the sense of ICH-E9 ([1](#)). It is used for demographics, baseline characteristics, and safety analyses including ECG, as well as for the description of biomarkers.
- **PK parameter analysis set (PKS):**  
The PK parameter analysis set (PKS) includes all patients from the TS receiving BI 754132 who provide at least one serum sample for determination of PK parameters that was not excluded due to a protocol deviation relevant to the evaluation of PK or due to PK non-evaluability (as specified below).  
It is used for the descriptive analyses of PK parameters.
- **DLE evaluable set (SRD part only):**  
The DLE evaluable set includes the patients from the TS who continued in the trial for at least 7 days after study drug administration and who attended Visits 2, 3, and 4, and the patients from the TS who were withdrawn from the trial before Visit 4 due to a DLE. It is used for the SMC outputs.

